**Cohort 3**

Assessment	Scr	Induction Phase						Maintenance Phase			Month 6 /EW
		Day 1  (Baseline)		Month 1		Month 2		Month 3	Month 4	Month 5	
		D0	D14	D0	D14	D0	D14				
Informed consent	X										
Medical & Ophthalmic history	X										
Vital signs/Physical exam 	X										X
12-Lead ECG	X										X
Tonometry  / Ophthalmologic examination 	X	X	X	X	X	X	X	X	X	X	X
Protocol refraction and VA using ETDRS chart 	X	X	X	X	X	X	X	X	X	X	X
Color fundus photography 	X	X 						X			X
Fluorescein angiography 	X	X 						X			X
SD-optical coherence tomography (SD-OCT) 	X	X 		X		X		X	X	X	X
Laboratory tests	X										X
Serum pregnancy test (if applicable)	X										
Reconfirmation of Eligibility		X									
Zimura™ 2 mg/eye Injection		X	X	X	X	X	X	X	X	X	
Lucentis® 0.5 mg/eye Injection		X	X	X	X	X	X	X	X	X	
3-Day Post-Injection Telephone Safety Check		X	X	X	X	X	X	X	X	X	
Concomitant medication assessment	X	X	X	X	X	X	X	X	X	X	X
Adverse events 		X	X	X	X	X	X	X	X	X	X

Day 1 Visit assessments should be performed within 14 days of Screening.

Physical examination is performed at Screening and at the Investigator's discretion thereafter. Vital Signs at all indicated timepoints.

Goldmann applanation tonometry must be performed at Screening, Day 1, and Month 6/EW. The Tono-Pen may be used at other times; however, Goldmann applanation tonometry must be used to verify any IOP ≥ 30mm Hg occurring more than 30 min post-injection, or any IOP ≥ 30 mmHg at any other time.

Tonometry should be measured prior to the first injection, after the first injection, and after the final injection and at any additional times as specified by the Intravitreal Administration Protocol (see Section 17.4).

Ocular assessments performed at Screening, Month 3, Month 6, and Early Withdrawal should be performed on both eyes (OU). Ocular assessments at all other study visits are performed on the study eye (SE) only.

All adverse events are to be recorded after first injection.

Imaging at Day 1 may be repeated if required per section 10.4.1.1 Reconfirmation of Eligibility at Day 1.

EW = Early Withdrawal Visit.

VISIT WINDOWS: It is essential that subjects adhere to their prescheduled study visits within the specified visit window outlined in section 10.4.

D0 = The first day of dosing at each monthly timepoint. D14 = The second day of dosing, 14 days after D0.

**Cohort 4**

Assessment	Scr	Induction Phase						Maintenance Phase						Month 6 /EW
		Day 1  (Baseline)		Month 1		Month 2		Month 3		Month 4		Month 5		
		D0	D14	D0	D14	D0	D14	D0	D2	D0	D2	D0	D2	
Informed consent	X													
Medical & Ophthalmic history	X													
Vital signs/Physical exam 	X													X
12-Lead ECG	X													X
Tonometry  / Ophthalmologic examination 	X	X	X	X	X	X	X	X	X	X	X	X	X	X
Protocol refraction and VA using ETDRS chart 	X	X	X	X	X	X	X	X	X	X	X	X	X	X
Color fundus photography 	X	X 						X						X
Fluorescein angiography 	X	X 						X						X
SD-optical coherence tomography (SD-OCT) 	X	X 		X		X		X		X		X		X
Laboratory tests	X													X
Serum pregnancy test (if applicable)	X													
Reconfirmation of Eligibility		X												
Zimura™ 2 mg/eye Injection		X	X	X	X	X	X	X	X	X	X	X	X	
Lucentis® 0.5 mg/eye Injection		X		X		X			X		X		X	
3-Day Post-Injection Telephone Safety Check		X	X	X	X	X	X		X		X		X	
Concomitant medication assessment	X	X	X	X	X	X	X	X	X	X	X	X	X	X
Adverse events 		X	X	X	X	X	X	X	X	X	X	X	X	X

Day 1 Visit assessments should be performed within 14 days of Screening.

Physical examination is performed at Screening and at the Investigator's discretion thereafter. Vital Signs at all indicated timepoints.

Goldmann applanation tonometry must be performed at Screening, Day 1, and Month 6/EW. The Tono-Pen may be used at other times; however, Goldmann applanation tonometry must be used to verify any IOP  $\geq$  30mm Hg occurring more than 30 min post-injection, or any IOP  $\geq$  30 mmHg at any other time.

Tonometry should be measured prior to the first injection, after the first injection, and after the final injection and at any additional times as specified by the Intravitreal Administration Protocol (see Section 17.4).

Ocular assessments performed at Screening, Month 3, Month 6, and Early Withdrawal should be performed on both eyes (OU). Ocular assessments at all other study visits are performed on the study eye (SE) only.

All adverse events are to be recorded after first injection.

Imaging at Day 1 may be repeated if required per section 10.5.1.1 Reconfirmation of Eligibility at Day 1.

EW = Early Withdrawal Visit.

VISIT WINDOWS: It is essential that subjects adhere to their prescheduled study visits within the specified visit window outlined in section 10.5.

D0 = The first day of dosing at each monthly timepoint. D2 = The second day of dosing, 2 days after D0. D14 = The second day of dosing, 14 days after D0.

## 3.2 DEFINITION OF POPULATIONS

The analysis and reporting of the data from this study will be performed using the following analysis populations:

### 3.2.1 Full Analysis Population

The Full Analysis Population will consist of all subjects enrolled in Cohort 1 or subjects randomized in Cohorts 2, 3, or 4 who did not fail screening.

### 3.2.2 Safety Population

The Safety population will include all subjects in the Full Analysis Population who received at least one study drug.

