11.4.4 Safety Analysis

The safety analysis will be conducted on all subjects who had at least one administration of the study drug.

Adverse events will be summarized using MedDRA terms. The incidence and severity of adverse events will be listed and grouped by body system.

All laboratory data will be listed and values falling outside normal ranges will be identified. Summary statistics (i.e., mean, median, standard deviation, minimum, and maximum) will be presented for all continuous variables.

Summary statistics will be given on the number of subjects for whom the trial medication had to be permanently stopped.

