### 2.3 SAMPLE SIZE AND RANDOMIZATION

As this study is not designed to perform formal hypothesis testing, there is no formal sample size calculation. The sample size selected is based on a reasonable number of subjects to understand the safety variables of the proposed regimen and to improve upon the study design prior to performance of controlled trials that may be initiated in the future. Approximately 60 subjects will be enrolled, 10 subjects each in cohorts 1, 2 and 20 subjects each in cohorts 3, 4.

Once all subjects have been enrolled in cohort 1, subjects will be centrally allocated to one of the three remaining treatment cohorts using a randomization list generated by a block randomization.

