## 4 STUDY SUBJECTS

### 4.1 DISPOSITION OF SUBJECTS

The number of subjects screened, assigned (if Cohort 1)/randomized (if Cohorts 2, 3, or 4), and treated will be presented. The reason for exclusion from one or more analysis sets will be summarized.

Disposition will be summarized for the Safety Population. The frequency and percentage of premature discontinuations from the study prior to Month 6 will be presented by cohort and overall. The primary reason for non-completion of the study will be summarized. The details of the ‘Adverse event’, ‘Protocol violation’, ‘Investigator decision’, ‘Sponsor decision’, ‘Subject request’, ‘Lost to follow-up’, ‘Subject non-compliance’ or ‘Other’ will be included in a listing.

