### 4.2 TREATMENT MISALLOCATIONS

For subjects with errors in treatment allocation, the following is described under which cohorts they will be reported for safety analyses:

For example, if subjects were:

- Assigned a cohort (regardless of error) but not treated, then they will be excluded for all safety analyses.
- For Cohorts 2, 3, and 4: Treated but not randomized, then by definition they will be reported under the cohort they actually followed for all safety analyses.

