## 7 SAFETY EVALUATION

All safety analyses will be performed on the Safety population. Missing values of safety data will not be imputed and safety summaries will be based on the observed cases.

[figure not shown]

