- Ocular TEAEs (study eye) leading to discontinuation of study drug
- TEAEs leading to death
- Study drug related TEAEs leading to death
- Injection procedure related TEAEs leading to death

Ocular TEAEs has been defined as TEAEs linked to the “Eye Disorders” system organ class and the ‘Intraocular pressure increased’ preferred term.

All AEs, including non-TEAEs, will be included in individual subject listings.

The listings will include the subject identifier, age, sex, verbatim term, preferred term, eye (N/A/OD/OS/OU), serious (yes/no), date of onset, relative study day of onset, duration of the event (or continuing), severity (mild/moderate/severe), causality (relationship to study drug/injection procedure), action taken (study drug permanently discontinued: yes/no), treatment (yes/no), and outcome (resolved /unresolved / fatal).

The same listings will be provided separately for severe AEs, AEs leading to permanent discontinuation of the study drug, and for AEs leading to death.

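### The SAP's Safety Population definition leaves out a Cohort 2–4 subject who was dosed without being randomized, contrary to SAP 4.2 and protocol 11.4.4

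*SAP*

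**What the plan says.** Three SAP sections together determine who enters the safety tables.

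- SAP 3.2.1 limits the Full Analysis Population to "all subjects enrolled in Cohort 1 or subjects randomized in Cohorts 2, 3, or 4 who did not fail screening".
- SAP 3.2.2 builds the safety set from it: "The Safety population will include all subjects in the Full Analysis Population who received at least one study drug".
- SAP 7 then states: "All safety analyses will be performed on the Safety population".

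Two other places set a different rule.

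- SAP 4.2, on allocation errors in Cohorts 2–4, covers subjects who were "Treated but not randomized, then by definition they will be reported under the cohort they actually followed for all safety analyses".
- Protocol 11.4.4 states: "The safety analysis will be conducted on all subjects who had at least one administration of the study drug". It sets no condition on randomization or screening.

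Neither document says which rule takes precedence. The readable text of SAP 8, which covers analyses not in the protocol, does not declare a narrower safety set.

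**The concern.** Safety is the trial's only objective, so the safety set is its main analysis population. For one kind of subject, dosed in Cohorts 2–4 without being randomized, the population definition and SAP 4.2 give opposite answers. A programmer who derives the safety flag from 3.2.2 excludes the subject; one who works from 4.2 includes the subject. The two would report different denominators, and possibly different event counts, from the same SAP.

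The adverse event tables are not the only outputs affected. The SAP also uses the Safety Population for disposition (4.1), the summary of significant protocol violations (4.3), the listing of unmet eligibility criteria (4.4), baseline characteristics (5) and medications (6). A subject dosed outside the randomization could therefore be missing from the violation summary as well.

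**Working it through.** **Planned sizes.** SAP 2.3 plans about 60 subjects, with "10 subjects each in cohorts 1, 2 and 20 subjects each in cohorts 3, 4". The sum is 10 + 10 + 20 + 20 = 60. The 50 subjects in Cohorts 2–4, split 1:2:2, give 50 × 1/5 = 10, 50 × 2/5 = 20 and 50 × 2/5 = 20. The plan's figures are consistent. There is no formal sample size calculation to reproduce.

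**Membership check.** The question is one of set membership. The screening clause in SAP 3.2.1 can be read as applying to all cohorts (reading A) or only to the randomized Cohorts 2–4 (reading B). For a subject who has been dosed:

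| Subject | SAP 3.2.1 + 3.2.2, reading A | Reading B | Protocol 11.4.4 |
|---|---|---|---|
| Cohort 1, passed screening | in | in | in |
| Cohort 1, screen failure | out | in | in |
| Cohorts 2–4, randomized, passed screening | in | in | in |
| Cohorts 2–4, randomized, screen failure | out | out | in |
| Cohorts 2–4, not randomized, passed screening | **out** | **out** | in |
| Cohorts 2–4, not randomized, screen failure | **out** | **out** | in |

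The bold rows are the point at issue. A dosed, non-randomized subject in Cohorts 2–4 is outside the Safety Population under either reading, while protocol 11.4.4 and SAP 4.2 both put that subject inside. Cohort 1 enters by enrollment, so the randomization condition does not touch it.

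The table also shows a related gap. The screening clause can remove a dosed subject who is classed as a screen failure, which again departs from the protocol's dosing-only rule.

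**Size, as an illustration.** Assume exactly one dosed, non-randomized subject, who has the only event in the cohort. The documents do not say whether that subject would count toward the planned size, so both cases are shown.

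| Assumption | Cohort | Subject included | Subject excluded |
|---|---|---|---|
| Additional to plan | 2 | 1/11 = 9.1% | 0/10 = 0% |
| Additional to plan | 3 or 4 | 1/21 = 4.8% | 0/20 = 0% |
| Within plan | 2 | 1/10 = 10.0% | 0/9 = 0% |
| Within plan | 3 or 4 | 1/20 = 5.0% | 0/19 = 0% |

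If there is no such subject, the effect is zero.

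**The case against.** The strongest reply is that SAP 4.2 already deals with this exact case. It is a specific rule, it covers all safety analyses just as SAP 7 does, and its other example excludes subjects who were assigned but never treated, so treatment is what decides. The verb in 3.2.2 could also be read as non-exhaustive, which would leave room for 4.2 to add the exceptional subject.

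This is good evidence of intent, but it does not remove the conflict. An inclusion statement in a population definition is ordinarily taken as complete. SAP 4.2 introduces itself as saying under which cohort a subject is reported; it assigns a column and does not amend 3.2.2.

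A second reply is that the consequence is small, and that is correct.

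- Cohorts 2–4 are allocated centrally from a randomization list, so the case requires an allocation error.
- No formal hypothesis testing is planned.
- SAP 7.4 keeps the events visible: "All AEs, including non-TEAEs, will be included in individual subject listings".
- SAP 4.1 presents the number treated and adds: "The reason for exclusion from one or more analysis sets will be summarized".

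Silent loss of the subject is therefore unlikely.

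A third reply is that the fix has a side effect: the Safety Population would no longer be a subset of the Full Analysis Population, and the number treated could exceed the number randomized. That is true, but it would describe correctly what had happened, and a footnote to the disposition table would explain it.

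**Conclusion.** The concern holds at low severity. For Cohorts 2–4, SAP 3.2.2 taken with 3.2.1 and 7 excludes a dosed, non-randomized subject from the safety summary tables, while SAP 4.2 and protocol 11.4.4 include that subject. The conclusion rests on reading 3.2.2 as a complete definition, and it does not depend on how the screening clause is read.

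The practical effect is conditional on such a subject existing. In the illustration, the choice of rule moves a cohort's incidence between 0% and 9.1–10.0% in Cohort 2, or between 0% and 4.8–5.0% in Cohort 3 or 4. Those figures assume one subject with the cohort's only event; they are not a forecast. Since the SAP provides a rule for this case, its population definition should agree with that rule.

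**What to change.** Restate SAP 3.2.2 along these lines:

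> *The Safety Population comprises every subject given at least one dose of study drug, whether or not the subject was randomized or passed screening. In Cohorts 2–4, a subject dosed without randomization is counted in the cohort whose regimen was followed (Section 4.2).*

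The reference to screening closes the related gap and follows from protocol 11.4.4, which asks only that a dose was given. A bare cross-reference from 3.2.2 to 4.2 would settle the randomization conflict but would leave the screening gap open.

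The cost is one restated SAP sentence. If a case arises, a footnote can explain a treated count above the randomized count. No new data are needed, and the grouping of randomized subjects does not change.

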## 3.3 DATA HANDLING CONVENTIONS

### 3.3.1 General Conventions

Data will be analysed using SAS (Version 9.4 or later) or R. Descriptive analyses will be performed on baseline, safety data. All tables will be created with the 4 dosing cohorts presented in columns, unless otherwise specified.

Descriptive statistics will be tabulated as follows:

- Categorical data will be summarized in contingency tables presenting frequencies and percentages.
- Continuous data will be summarized using number of non-missing values (n), mean, standard deviation, median, minimum, 1st quartile (Q1), 3rd quartile (Q3), and maximum values.

Listings with individual Subjects' data will be provided for all CRF (including derived data) and central laboratory data or other external data. Data collected on the CRF that are *not* present in a table will also be listed (e.g. time and method of tonometry, comments fields, data on Fatal Outcomes page, Unscheduled Visit pages, etc.).

### **3.3.2 Visit Windows**

The scheduled visits will be used in the analyses over time.

Missing scheduled follow-up visits will be substituted by an unscheduled or early withdrawal visit occurring within each follow-up visit window, if there is only one unscheduled or early withdrawal visit occurring within the window. If there are multiple unscheduled or early withdrawal visits occurring within the window, the closest one within the visit window will be used. If no unscheduled or early withdrawal visit occurred within the window, the visit will be considered as missing. The details are tabulated in **Appendix 1**.

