### **Intraocular Pressure.**

The Baseline intraocular pressure within an eye will be determined as the average of the Screening and Day 1 (also called Baseline in the protocol) pre-injection measurements. Non-integer values for the average will be rounded up prior to subsequent calculations of change from baseline.

IOP will be summarized by visit, including all pre-injection, “IOP after first injection” and “IOP after second injection” measurements. An additional tabular summary of the percentage of subjects in categories of IOP will be presented by cohort, visit, and injection time (pre-injection, IOP after first injection, IOP after second injection).

“IOP after first/second injection” is defined as the IOP measurement that is closest in time to the protocol-specified post-injection timepoint (but at least 25 minutes post-injection). If there are two closest measurements equidistant to this timepoint, then the measurement after the protocol-specified timepoint will be used.

Mean IOP over time of all scheduled measurements (pre-injection, IOP after first injection, and IOP after second injection) will be plotted.

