## **7.8 CLINICAL LABORATORY DETERMINATION**

All laboratory data will be listed and values falling outside normal ranges will be identified, whether they will be deemed clinically relevant or not.

- Laboratory data will also be summarized in tables presenting values at each scheduled visit up through the Month 6 visit (mean, SD, median, minimum, Q1, Q3, maximum, N)
- Value changes from Baseline to each scheduled visit up through the Month 6 visit (mean, SD, median, minimum, Q1, Q3, maximum, N)

for the following parameters: Hematological parameters (Hemoglobin, White blood cells, Platelets, Neutrophils (absolute numbers), Lymphocytes (absolute numbers), Monocytes (absolute numbers), Eosinophils (absolute numbers), Basophils (absolute numbers)), Biochemical parameters (Sodium, Potassium, Chloride, Bicarbonate, Calcium, Phosphorus Inorganic, Creatinine, Urea Nitrogen, Total bilirubin, GGT, Alkaline phosphatase, SGOT/AST, SGPT/ALT).

The incidence of subjects with “Notable Laboratory Values” after the first dose of study drug will be evaluated using the criteria for Notable Laboratory Values given below.

By-subject listings of all notable laboratory values will also be provided; for each subject who has an analyte with a notable value, all values of that particular analyte taken during the study will be presented in the listing, and the notable value, and any values outside of normal limits, will be identified.

For this “Notable Laboratory Values” analysis, *all* laboratory values after randomization will be taken in account, i.e., any values obtained after Day 1, at unscheduled visits, as well as values from

the regularly scheduled laboratory visit at Month 6. Three Notable Laboratory Values tables and accompanying by-subject listings will be presented: (1) notable abnormalities for subjects with normal Baseline results, (2) notable abnormalities for subjects with abnormal Baseline results and (3) notable abnormalities without regard to Baseline abnormalities (i.e., normal or abnormal Baseline results). The table without regard to Baseline abnormalities will be a composite of the previous two tables (normal Baseline, abnormal Baseline).

Lab analytes and primary criteria used for Notable Laboratory Values:

a. HEMATOLOGY

- i. Hemoglobin  $< 0.75x$  baseline
- ii. Platelets  $< 75$  or  $> 750$  ( $10^9/L$ )
- iii. WBC count  $< 2.5$  or  $> 17.5$  ( $10^9/L$ )
- iv. Neutrophils (absolute)  $< 0.5x$  LLN or  $> 1.5x$ ULN

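### Measured IOP is tabulated only by visit and injection time, so no planned table gives the number of subjects whose measured IOP was ever raised; the adverse event count is a partial substitute

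*SAP*

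**What the plan says.** The intraocular pressure part of SAP 7.7 plans three displays:

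- a summary of values by visit, covering pre-injection and post-injection readings;
- a category table: "An additional tabular summary of the percentage of subjects in categories of IOP will be presented by cohort, visit, and injection time";
- a plot: "Mean IOP over time of all scheduled measurements".

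Each post-injection value is a single selected reading, the one nearest the protocol timepoint "but at least 25 minutes post-injection". The section defines neither the IOP categories nor any maximum, worst-value or any-time count.

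On which visits count, SAP 3.3.2 says "The scheduled visits will be used in the analyses over time". It then allows one exception: "Missing scheduled follow-up visits will be substituted by an unscheduled or early withdrawal visit occurring within each follow-up visit window". If several such visits fall in a window, the closest is used.

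Two other routes carry IOP data. SAP 3.3.1 lists by subject the CRF data that are not in tables, including "time and method of tonometry, comments fields, data on Fatal Outcomes page, Unscheduled Visit pages". SAP 7.4 adds the preferred term "Intraocular pressure increased" to its definition of ocular treatment-emergent events, and its tables count a subject once per preferred term.

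For notable laboratory values, SAP 7.8 works per subject and takes in "any values obtained after Day 1, at unscheduled visits".

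**The concern.** The trial compares regimens that differ in how many injections the eye receives and whether they fall on the same day. A reader will want to know what fraction of subjects in each cohort had a raised IOP at any time. A by-visit table answers a different question: what fraction was raised at this visit, on the selected reading.

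Two kinds of reading can miss the IOP tables. Protocol 7.2 requires IOP to come down to stated limits before a second same-day injection and before the subject leaves the clinic, so a high value leads to repeat readings, of which one is kept. A rise that prompts an unscheduled visit and settles before the next scheduled one is also left out if the scheduled visit took place. These are readings taken because something needed checking.

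**Working it through.** The plan states no figure on this point, so there is none to reproduce. The check has three parts.

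**1. Scheduled injection visits and injections per subject** (Protocol Section 3 and 11.1)

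| Cohort | n | Injection visits | Injections (one post-injection reading each) |
|---|---|---|---|
| 1 | 10 | 6 × 2 = 12 | 6 × (1 + 2) = 18 |
| 2 | 10 | 6 | 6 × 2 = 12 |
| 3 | 20 | 3 × 2 + 3 = 9 | 3 × (2 + 1) + 3 × 2 = 15 |
| 4 | 20 | 3 × 2 + 3 × 2 = 12 | 3 × (2 + 1) + 3 × (1 + 2) = 18 |

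**2. What by-visit percentages leave open**

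Suppose the table shows exactly one affected subject at each of k injection visits. If it is always the same subject, 1 subject was ever affected. If it is a different subject each time, the number is min(k, n).

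- Cohort 1: 1 to min(12, 10) = 10 of 10
- Cohort 2: 1 to min(6, 10) = 6 of 10
- Cohort 3: 1 to min(9, 20) = 9 of 20
- Cohort 4: 1 to min(12, 20) = 12 of 20

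The same point in rates, with an **assumed** per-visit rate p, constant over visits. If the same subjects are affected every time, the any-time proportion is p. If visits are independent, it is 1 − (1 − p)^k.

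| Assumed p | Cohorts 1 and 4 (k = 12) | Cohort 2 (k = 6) | Cohort 3 (k = 9) |
|---|---|---|---|
| 2% | 21.5% | 11.4% | 16.6% |
| 5% | 46.0% | 26.5% | 37.0% |
| 10% | 71.8% | 46.9% | 61.3% |

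For example, 1 − 0.95^12 = 46.0% and 1 − 0.95^6 = 26.5%. At p = 5%, identical by-visit columns could stand for 5% of subjects in every cohort, or for 46.0% in Cohort 1 against 26.5% in Cohort 2.

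**3. Following one unscheduled reading through the SAP**

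Take a Cohort 2 subject who attends Month 2 and Month 3 with unremarkable readings and has a high IOP at an unscheduled visit between them.

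- IOP tables (SAP 7.7 with 3.3.2): not included, because no scheduled visit is missing.
- IOP plot: not included, because it uses scheduled measurements.
- Adverse event tables (SAP 7.4): included only if the reading was reported as an event. Protocol 12.1 ties that to symptoms, intervention, a change in dosing or treatment, a serious outcome, or the judgement of the investigator or sponsor.
- Listings (SAP 3.3.1): included.

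A reading at or above 30 mmHg that met none of the Protocol 12.1 criteria would therefore be listed but counted nowhere.

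**The case against.** The strongest reply is that the adverse event tables already do the job. They are per subject, cover the whole treatment-emergent period, are not tied to visits, and are split by eye, relatedness and maximum severity. The SAP adds the raised-IOP term by name. A reader might therefore infer too much in saying that no table at all shows who ever had a raised IOP. The documents do not support that: the gap concerns measured readings. What survives is that event reporting depends partly on judgement, so it is not an incidence at a fixed threshold.

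A reader might also infer that unscheduled readings are lost. They are not. They can replace a missing scheduled visit, and they are listed. With 10 or 20 subjects per cohort someone could count from the listings, but a listing is not a planned summary. The continuous summaries include a maximum at each timepoint, which shows the highest selected reading but not how many subjects were affected over time.

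The ranges above are illustrations. If one subject is affected in a single cell of Cohort 1 and no other cell is positive, the any-time proportion from selected readings is exactly 10%; if all cells are zero, it is zero. The counting bounds are also by visit, while the table splits further by injection time.

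Finally, the contrast with laboratory values is not a contradiction. Laboratory tests have one scheduled post-baseline visit, Month 6, plus Day 9 for the first 3 to 6 Cohort 1 subjects, whereas tonometry is done at every visit. SAP 7.8 serves as a precedent for per-subject counting from all values, not as proof of an error.

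**Conclusion.** The point holds in a limited form. Measured IOP has no any-time or maximum summary per subject, unscheduled and non-selected readings reach the IOP tables only by exception, and the adverse event count replaces the missing figure only in part. This is a reporting gap, not a bias in a test, since the study is descriptive. Its size cannot be estimated because the documents give no IOP event rate. The 1-to-10 and 1-to-6 ranges rest on a hypothetical pattern of one affected subject per injection visit, and the rate table on assumed rates with either complete repetition in the same subjects or independence between visits. Appendix 1 is not visible in the available text, so window widths could not be checked; they do not alter the rule that an attended scheduled visit excludes the unscheduled one. The change is worth making because safety is the sole objective and the regimens range from 6 to 12 injection visits.

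**What to change.** Add to SAP 7.7 a table by cohort, on the Safety population, of each subject's maximum study-eye IOP and maximum rise from Baseline after the first injection. Use all scheduled, repeat, unscheduled and Early Withdrawal readings, following the approach of SAP 7.8. Show injection-day post-injection readings separately from all others.

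Report the number and percentage of subjects:

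- at or above 30 mmHg, the level at which Protocol 7.2 calls for verification by Goldmann tonometry, subject to its rule on time since injection;
- with a rise of 15 mmHg or more, labelled as a descriptive cut-off. It must not be presented as the dose-limiting toxicity criterion of Protocol 9.2.3.1, which needs two examinations at least one day apart, excludes the injection day, and applies despite pharmaceutical intervention.

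State the categories for the by-visit IOP table at the same time. Optionally, add a worst-value row, including unscheduled visits, for anterior chamber cells and vitreous haze beside the shift tables already planned in SAP 7.7.

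The cost is SAP wording and one or two descriptive tables. No new data collection is needed, and no clinical rule changes.
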